9.2 Other Medical Device or Medication Specified for Use During the Study

No other medical devices or medications are required to be used in conjunction with the treatments during the clinical study.

9.3 Treatment Assignment / Randomization

Subjects will be randomized in a 1:1 ratio to receive treatment (lens) in crossover sequence of Test product then Comparator product or Comparator product then Test product, respectively.

Sequence	EDC/randomization integration system	Lens Name
Sequence 1	LID205255/Biofinity Toric	[REDACTED] Toric/Biofinity Toric
Sequence 2	Biofinity Toric/ LID205255	Biofinity Toric/[REDACTED] Toric

Only after signing the ICF, a subject will be assigned a subject number by the electronic data capture system.

A randomization list will be generated using a validated system that automates the random assignment of treatment arms to randomization numbers in the specified ratio. Subjects will be assigned treatment according to the randomization list uploaded in the randomization system. The randomization list will be generated and maintained by the study sponsor.

[figure not shown]
At Visit 1, all eligible subjects will be randomized via the EDC/randomization integration to one of the treatment arms. The investigator’s delegate will access the respective system after

[figure not shown]
confirming that the subject meets all the eligibility criteria. A randomization number will be automatically assigned to the subject according to the subject randomization list but will not be communicated to the site user. The EDC/randomization integration system will inform the site user of the treatment sequence (lens sequence) assignment to be dispensed to the subject.

9.4 Treatment masking

This study is double-masked, with subjects randomized in a 1:1 ratio to receive [REDACTED] Toric and Biofinity Toric contact lenses in a crossover sequence for the duration of the two 30-day treatment period. [REDACTED]

[REDACTED]

[REDACTED] Unmasking will occur only after all planned study data have been validated, and the database locked.

Masked study personnel must avoid seeking information that may compromise masking.

[REDACTED]
[REDACTED]
[REDACTED]

In the event of a medical emergency where the knowledge of subject treatment is required, an individual investigator will have the ability to unmask the treatment assignment for a specific subject after contacting an appropriate study sponsor representative if time allows.

9.5 Accountability Procedures

Upon receipt of the IPs, the investigator or delegate must conduct an inventory. [REDACTED]
[REDACTED]

[REDACTED] Throughout the study, the investigator or delegate must maintain records of IP dispensation and collection for each subject. This record

must be made available to the study monitor for the purposes of verifying the accounting of IP supplies. Any discrepancies and/or deficiencies between the observed disposition and the written account must be recorded along with an explanation. All IPs sent to the investigator must be accounted for by study sponsor personnel, and in no case be used in an unauthorized situation.

The investigator should make every effort to collect unused lenses, foils, and supplies from subjects.

It is the investigator's responsibility to ensure that:

- All study products are accounted for and not used in any unauthorized manner
- All unused products are available for return to the study sponsor, as directed
- Any study lenses associated with a device deficiency or with any product-related adverse event (i.e., ADE or SADE) are returned to the study sponsor for investigation, unless otherwise directed by the sponsor. Refer to Section 11 of this protocol for additional information on the reporting of device deficiencies and AEs and the return of study products associated with these events.

The investigator is responsible for proper disposition of all unused IPs at the conclusion of the study, according to the instructions provided in the MOP.

9.6 Changes to concomitant medications, treatments/ procedures

After the subject is enrolled into the study, the investigator must instruct the subject to notify the study site about:

- Any new medications
- Alterations in dose or dose schedules for current medications,
- Any medical procedure or hospitalization that occurred or is planned
- Any nondrug therapies (including physical therapy and blood transfusions).

The investigator must document this information in the subject's case history source documents.

10 STUDY PROCEDURES AND ASSESSMENTS

10.1 Informed Consent and Screening

The investigator or delegate must explain the purpose and nature of the study, and have the subject read, sign, and date the IRB/IEC-approved informed consent document. The subject must sign the ICF BEFORE any study-specific procedures or assessments can be performed, including study-specific screening procedures. Additionally, have the individual obtaining consent from the subject and a witness, if applicable, sign and date the informed consent document.

The investigator or delegate must provide a copy of the signed document to the subject and place the original signed document in the subject's chart, or provide documentation as required by local regulations.

10.2 Description of Study Procedures and Assessments

Detailed descriptions of assessments and procedures are provided in the MOP. The investigator is responsible for ensuring responsibilities for all procedures and assessments are delegated to appropriately qualified site personnel.

10.2.1 Demographics

Obtain demographic information including age, race, ethnicity, and sex.

10.2.2 Medical History

Collect medical history information, including information on all medications used within the past 30 days. Include herbal therapies, vitamins, and all over-the-counter as well as prescription medications. Throughout the subject's participation, obtain information on any changes in medical health and/or the use of concomitant medications.

Medical History and Concomitant Medications will be collected in the eCRF as outlined in the MOP.

10.2.3 Investigational Product compliance

Review subject compliance with the IP usage and adjunct product usage and collect all used and unused study IPs and other products that were dispensed.

10.2.4 Adverse Event Collection: Safety Assessment

Assess and record any adverse events that are observed or reported since the previous visit, including those associated with changes in concomitant medication dosing.

10.2.5 Slit Lamp Biomicroscopy: Safety Assessment

SLE of the cornea, iris/anterior chamber and lens must be performed in both eyes before instillation of any diagnostic eye drops.

10.2.6 Device Deficiencies: Safety Assessment

Assess and record any Device Deficiencies that are reported or observed since the previous visit. Requirements for reporting device deficiencies in the study can be found in Section 11.

10.3 Unscheduled Visits

If a subject visit occurs between any regularly scheduled visit and the visit is conducted by study personnel, this visit must be documented as an Unscheduled Visit. If the subject seeks medical attention outside the clinic (for example, at an Emergency Room) or at the clinic but is seen by nonstudy personnel, the investigator is to capture adverse event-related information on the Adverse Event form upon becoming aware.

During all unscheduled visits, the investigator must conduct the following procedures:

- Collect Adverse Event information
- Collect device deficiency information
- Record changes in medical condition or concomitant medication
- Perform a biomicroscopy
- VA w/study lenses (OD, OS, logMAR distance)

The investigator may perform additional procedures for proper diagnosis and treatment of the subject. The investigator must document this information in the subject's case history source documents.

If during an Unscheduled Visit the subject is discontinuing the IP or discontinuing from the study, the investigator must conduct Exit procedures according to [Table 3–1](#) Schedule of Study Procedures and Assessments and Section 10.4.3, as possible.

10.4 Discontinued Subjects

10.4.1 Screen Failures

Subjects who were excluded from the study after signing the informed consent and prior to, randomization to product/dispense of study product.

The investigator must document the reason for screen failure in the subject's case history source documents.

Subject numbers must not be reused.

10.4.2 Discontinuations

Discontinued subjects are individuals who voluntarily withdraw or are withdrawn from the study by the investigator after signing informed consent.

Subject numbers of discontinued subjects must not be re-used (i.e., subject replacement is not allowed).

Subjects may discontinue from study or study treatment at any time for any reason. Subjects may also be discontinued from study treatment at any time if, in the opinion of the investigator, continued treatment poses a risk to their health.

If a subject discontinues from study treatment, every effort must be made to keep the subject in the study and to continue with the study assessments as specified in the schedule of study procedures and assessments until the final visit.

For subjects discontinuing from the study, the investigator must complete all Exit procedures according to [Table 3–1](#) Schedule of Study Procedures and Assessments and [Section 10.4.3](#), if the subject is willing and able, and if in the opinion of the investigator it is safe for the subject to do so.

The investigator must document the reason for study or treatment discontinuation in the subject's case history source documents.

To ensure the safety of all subjects who discontinue early, investigators must assess each subject and, if necessary, advise them of any therapies and/or medical procedures that may be needed to maintain their health.

10.4.3 Schedule of Procedures and Assessments for Subjects Discontinued from Investigational Product

Other than screen failures, if a subject discontinues from the study, the subject should undergo an Early Exit Visit. Refer to [Table 3–1](#).

10.5 Clinical Study Termination

The study sponsor reserves the right to suspend or close the investigational site or suspend or terminate the study in its entirety at any time.

If the clinical study is prematurely terminated or suspended by the study sponsor:

- The study sponsor must:
 - Immediately notify the investigator(s) and subsequently provide instructions for study termination.
 - Inform the investigator and the regulatory authorities of the termination/suspension and the reason(s) for the termination/suspension.
- The investigator must:
 - Promptly notify the IRB/IEC of the termination or suspension and of the reasons.
 - Provide subjects with recommendations for post-study treatment options as needed.

The investigator may terminate the site’s participation in the study for reasonable cause.

Breaking of the masked treatment codes will be done after locking the database.

10.5.1 Follow-up of subjects after study participation has ended

Following this study, the subject will return to their eye care professional for their routine eye care.

11 ADVERSE EVENTS AND DEVICE DEFICIENCIES

11.1 General Information

An AE is any untoward medical occurrence, unintended disease or injury, or untoward clinical signs (including abnormal laboratory findings) in subjects, users, or other persons,

whether or not related to the investigational medical device (test product). Refer to the Glossary of Terms and figures below for categories of AEs and SAEs.

Figure 11–1 Categorization of All Adverse Events

[figure not shown]
[figure not shown]

Figure 11–2 Categorization of All Serious Adverse Events

Specific Events Relevant to this Protocol

Serious Adverse Events

In addition to reporting all AEs (serious and nonserious) meeting the definitions, the investigator must report any occurrence of the following as an SAE:

- An ocular infection including a presumed infectious ulcer with any of the following characteristics:
 - Central or paracentral location
 - Penetration of Bowman's membrane
 - Infiltrates >2 mm diameter
 - Iritis
 - Increase in intraocular pressure
 - Culture positive for microorganisms
 - Increasing size or severity at subsequent visits
- Any central or paracentral corneal event (such as neovascularization) that results in permanent opacification
- Hypopyon
- Hyphema
- Neovascularization within the central 6 mm of the cornea
- Permanent vision loss as defined by loss of 2 or more lines of Distance BCVA from enrollment visit that fails to resolve
- Uveitis (anterior, intermediate, or posterior)
- Corneal abrasion affecting $\geq 50\%$ of corneal surface area

Significant Nonserious Adverse Events

A significant nonserious AE is a device-related, non-sight-threatening adverse event that warrants discontinuation of any contact lens wear for greater than or equal to 2 weeks. In addition, the investigator must report any occurrence of the following as a Significant Nonserious Adverse Event:

- Peripheral nonprogressive noninfectious ulcers
- All symptomatic corneal infiltrative events
- Corneal staining score greater than or equal to grade 3 (Refer to MOP for grading scales)

- Temporary vision loss as defined by loss of 2 or more lines of Distance BCVA from enrollment visit that persists for 2 or more weeks
- Neovascularization score greater than or equal to grade 2 (Refer to MOP for grading scales)

The above events are based on the categories provided in the ISO 11980 and the US FDA Premarket Notification (510(k)) Guidance Document for Daily Wear Contact Lenses.

Device Deficiencies

A device deficiency is inadequacy of a medical device with respect to its identity, quality, durability, reliability, safety, or performance. A device deficiency may or may not be associated with patient harm (i.e., ADE or SADE); however, not all ADEs or SADEs are due to a device deficiency. The investigator should determine the applicable category listed in the Device Deficiency eCRF for the identified or suspect device deficiency and report any patient harm separately. Examples of device deficiencies include the following:

- Failure to meet product specifications (e.g., incorrect lens power/diameter/base curve/color)
- Lens/solution cloudy
- Lens surface/edge defect
- Torn lens during handling/in pack
- Packaging deficit (e.g., mislabeled product, tampered seal, leaking bottle/container)
- Suspect product contamination

11.2 Monitoring for Adverse Events

At each visit, after the subject has had the opportunity to spontaneously mention any problems, the investigator should inquire about AEs by asking the standard questions shown below and report as applicable:

- “Have you had any health problems since your last study visit?”
- “Have there been any changes in the medicines you take because of a new health issue since your last study visit?”

In addition, changes in biomicroscopy findings [REDACTED] evaluated during the study are to be reviewed by the investigator. Any untoward (unfavorable and unintended) change in a biomicroscopy parameter [REDACTED] that is clinically relevant, in

the opinion of the investigator, is to be reported as an AE. These clinically relevant changes will be reported regardless of causality.

11.3 Procedures for Recording and Reporting

AEs are collected from the time of informed consent Any pre-existing medical conditions or signs/symptoms present in a subject prior to the start of the study (i.e., before informed consent is signed) are not considered AEs in the study and should be recorded in the Medical History section of the eCRF.

For each recorded event, the ADEs and SAEs documentation must include: date of occurrence, severity, treatment (if applicable), outcome, and assessments of the seriousness and causality. In addition, the investigator must document all device deficiencies reported or observed with test and comparator products on the Device Deficiency eCRF. The site must submit all available information on ADEs, SAEs, and device deficiencies to the Study Sponsor immediately as follows:

- ADEs or SAEs are documented on the *Serious Adverse Event and Adverse Device Effect* eCRF within 24 hours of the investigator's or site's awareness.
- Device deficiencies are documented on the *Device Deficiency* eCRF within 24 hours of the investigator's or site's awareness.
- Additional relevant information after initial reporting must be entered into the eCRF as soon as the data become available.
- Document any changes to concomitant medications on the appropriate eCRFs.
- Document all relevant information from Discharge Summary, Autopsy Report,
- Certificate of Death etc., if applicable, in narrative section of the *Serious Adverse Event and Adverse Device Effect* eCRF.

Note: Should the EDC system become nonoperational, the site must complete the appropriate paper *Serious Adverse Event and Adverse Device Effect* and/or *Device Deficiency* Form. The completed form is emailed to the Study Sponsor at [contact] according to the timelines outlined above; however, the reported information must be entered into the EDC system once it becomes operational.

Any AEs and device deficiencies for nonstudy marketed devices/products (i.e. CLEAR CARE contact lens solution) will be considered and processed as spontaneous (following the postmarket vigilance procedures) and should be communicated to the device's/product's manufacturer as per local requirements.

Study Sponsor representatives may be contacted for any protocol related question and their contact information is provided in the Manual of Procedures that accompanies this protocol.

Further, depending upon the nature of the AE or device deficiency being reported, the Study Sponsor may request copies of applicable portions of the subject's medical records. The investigator must also report all AEs and device deficiencies that could have led to a SADE according to the requirements of regulatory authorities or IRB/IEC.

Intensity and Causality Assessments

Where appropriate, the investigator must assess the intensity (severity) of the AE based on medical judgment with consideration of any subjective symptom(s), as defined below:

Intensity (Severity)

- | | |
|----------|--|
| Mild | An AE is mild if the subject is aware of but can easily tolerate the sign or symptom. |
| Moderate | An AE is moderate if the sign or symptom results in discomfort significant enough to cause interference with the subject's usual activities. |
| Severe | An AE is severe if the sign or symptom is incapacitating and results in the subject's inability to work or engage in their usual activities. |

For every AE in the study, the investigator must assess the causality (Related or Not Related to the medical device or study procedure). An assessment of causality will also be performed by Study Sponsor utilizing the same definitions, as shown below:

Causality

- | | |
|---------|--|
| Related | An AE classified as related may be either definitely related or possibly related where a direct cause and effect relationship with the medical device or study procedure has not been demonstrated, but there is a reasonable possibility that the AE was caused by the medical device or study procedure. |
|---------|--|

Not Related An AE classified as not related may either be definitely unrelated or simply unlikely to be related (i.e., there are other more likely causes for the AE).

The Study Sponsor will assess the AEs and may upgrade the investigator's assessment of seriousness and/or causality. The Study Sponsor will notify the investigator of any AEs that is upgraded from nonserious to serious or from unrelated to related.

11.4 Return product analysis (as applicable)

Study Sponsor representatives and their contact information are provided in the MOP that accompanies this protocol.

Alcon study products associated with device deficiencies and/or product related AEs should be returned and must include the Complaint # which will be provided by Study Sponsor after the case is entered in the Study Sponsor's Global Product Complaint Management System (GPCMS) after the database lock.

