8 STUDY POPULATION

The study population consists of volunteer subjects aged 18 or over who are habitual toric weekly/monthly soft contact lens wearers, have at least 3 months of contact lens wearing experience, and who wear their habitual lenses at least 5 days per week and at least 10 hours per day. It is aimed to enroll (consent) approximately 72 subjects at approximately 6 sites in the United States, with a target of 58 total subjects completed. Site-specific targets may vary based upon individual site capabilities. Estimated time needed to recruit subjects for the study is approximately 8 weeks; however, unanticipated circumstances may shorten or lengthen this time and would not require amendment of this protocol.

2. Any use of systemic or ocular medications for which contact lens wear could be contraindicated, as determined by the investigator.
3. History of refractive surgery or plan to have refractive surgery during the study or irregular cornea in either eye.
4. Ocular or intraocular surgery (excluding placement of punctal plugs) within the previous 12 months or planned during the study.
5. Biomicroscopy findings at screening that are moderate (Grade 3) or higher and/or corneal vascularization that is mild (Grade 2) or higher; presence of corneal infiltrates
6. Current or history of pathologically dry eye in either eye that, in the opinion of the investigator, would preclude contact lens wear.
7. Current or history of herpetic keratitis in either eye.
8. Eye injury in either eye within 12 weeks immediately prior to enrollment for this trial.
9. Current or history of intolerance, hypersensitivity or allergy to any component of the study products.
10. Any use of topical ocular medications and artificial tear or rewetting drops that would require instillation during contact lens wear.
11. The investigator, his/her staff, family members of the investigator, family members of the investigator's staff, or individuals living in the households of the aforementioned persons may not participate in the study.
12. Participation of the subject in a clinical trial within the previous 30 days or currently enrolled in any clinical trial.
13. Monovision and multifocal contact lens wearers.
14. Daily Disposable contact lens wearers
15. Habitual Biofinity Toric/Biofinity Toric XR contact lens wearers in the past 3 months prior to consent.

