11.5 Unmasking of the Study Treatment

Masked information on the identity of the assigned medical device should not be disclosed during the study (See Section 9.4 for details on the masking procedure). If the treatment code needs to be broken in the interest of subject safety, the investigator is encouraged to contact an appropriate Study Sponsor representative prior to unmasking the information if there is sufficient time. Dependent upon the individual circumstances (i.e., medical emergency), the code may be broken prior to contact with the Study Sponsor. The Study Sponsor must be informed of all cases in which the code was broken and of the circumstances involved. Additionally, the Study Sponsor may be required to unmask the information in order to fulfill expedited regulatory reporting requirements.

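### Protocol Section 11.4 holds the sponsor's analysis of a returned test lens until after database lock, with no exception for serious device effects.

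*Protocol*

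**What the plan says.** Protocol Section 11.4 sets the condition for a return: "Alcon study products associated with device deficiencies and/or product related AEs should be returned and must include the Complaint" number. It then says when that number exists. A return "must include the Complaint # which will be provided by Study Sponsor after the case is entered" in the sponsor's complaint system, and that step is placed after lock: "Global Product Complaint Management System (GPCMS) after the database lock".

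Section 9.5 makes the investigator responsible for seeing that any study lens associated with a device deficiency or a product-related event (ADE or SADE) goes back. Such lenses "are returned to the study sponsor for investigation, unless otherwise directed by the sponsor". It sets no time and points onward for the procedure: "Refer to Section 11 of this protocol for additional information on the reporting of device deficiencies and AEs and the return of study products".

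Section 11.3 gives the site 24 hours from awareness to enter ADEs, SAEs and device deficiencies in the eCRF. Section 11.5 keeps the treatment code closed in general but notes that "the Study Sponsor may be required to unmask the information in order to fulfill expedited regulatory reporting requirements".

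**The concern.** The return exists so that the sponsor can investigate the lens. In 11.3 the protocol treats device-related and serious events as urgent. In 11.4 it defers the physical evidence on them to a time when no subject is wearing a study lens.

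For some deficiencies listed in 11.1, such as suspected contamination or a wrong lens power, the lens itself is direct evidence. The glossary recognises that a signal from a deficiency may call for prompt action to protect other subjects. Section 11.3 has the sponsor make its own causality assessment of adverse events, and 10.5 lets it suspend the study. For a serious device effect it would take those decisions without its own examination of the lens, and nothing in 11.4 separates such a case from a lens torn in handling.

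**Working it through.** The plan states no figure on this point. The check is mainly a reading of the sections together, with one calculation for scale.

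**1. Is there an earlier route for the return?**
- Section 9.5 requires the return but refers to Section 11 for how it is done.
- Within Section 11, only 11.4 deals with returns, and it makes the complaint number mandatory.
- The reference to lock can be attached to the entry of the case or to the issue of the number. Either way the number is not available before lock.
- The sponsor's power in 9.5 to direct otherwise concerns whether a lens is returned. It does not waive the number or bring it forward.

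**2. Where does lock fall?**
- Section 11.6 equates lock with study completion.
- Section 9.4 places general unmasking after all planned data have been validated and the database locked.
- The glossary ties study completion to the last subject's last visit or a decision to terminate, whichever is later.
- In a study run as planned, lock therefore follows the last subject's exit.

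**3. How long could a lens wait?**

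Inputs:
- Recruitment R = 8 weeks = 56 days (Section 8: "Estimated time needed to recruit subjects for the study is approximately 8 weeks").
- Wear period w = 30 days per lens, with a visit window of −1/+3 days, so 29 to 33 (Table 3–1).
- Assumptions: lenses are dispensed on the day of enrollment, there is no gap between periods, and the last subject enrolls at the end of week 8.

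For an event on wear day d in a subject enrolled on day e, the wait until the last subject's exit is (R − e) + 2w − d.

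| Event | w = 29 | w = 30 | w = 33 |
|---|---|---|---|
| First subject, first days (e = 0, d ≈ 0) | 56 + 58 = 114 days | 56 + 60 = 116 days | 56 + 66 = 122 days |
| Last subject, first days (e = 56, d ≈ 0) | 58 days | 60 days | 66 days |
| Last subject, last day (e = 56, d = 2w) | 0 days | 0 days | 0 days |

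The time from last exit to lock is not given and is added in every row. So are any gaps between visits, which are redacted. Section 8 says recruitment may run shorter or longer; each week of change moves the first row by 7 days.

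**4. Does 11.5 already cover serious cases?** It allows the sponsor to unmask for expedited reporting. It says nothing about the lens or the complaint number, so the condition in 11.4 still applies.

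**The case against.** The strongest defence is masking. Section 11.4 gives complaint numbers to Alcon products only, so a number issued during the study tells anyone who sees it that the lens was the test lens. The documents do not give this as the reason, but it is a sound one for routine nonserious returns, and it argues against removing the reference to lock for every case. It is weaker for serious device effects, where 11.5 already accepts some unmasking.

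The second defence is that the delay touches one source of evidence, and this stands. Reports still arrive within 24 hours. The test lens foil carries the lot number and dispensing is recorded per subject (Table 9–1, Section 9.5). The study can be suspended (10.5) and the code broken in an emergency (11.5). A reader might infer that a lot defect could not be found, or that no subject could be protected, until everyone had been exposed. The documents do not support that: nothing stops the sponsor from tracing a lot or testing other lenses from it.

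Three other stronger readings also fail:
- *The sponsor is the only safety oversight because there is no data monitoring committee.* Section 11.3 also requires reporting as regulators and ethics boards demand, and Section 14 gives those boards safety updates and progress reports.
- *The safety tables would rest on uninformed causality entries.* No adverse event table in SAP Section 5.3.1 is split by relatedness. Causality enters only through the definition of significant nonserious events, and several events are placed there whatever their cause.
- *Sections 9.5 and 11.4 flatly contradict each other on the comparator.* Section 11.6 sends complaints on non-Alcon products to their manufacturer, which partly explains the narrower scope of 11.4. It covers complaints rather than physical return, so a wording gap remains.

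Finally, the Manual of Procedures is not available and may hold an interim route. Section 11.4 cites it only for contact details.

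**Conclusion.** The point holds in a limited form. On the current, unredacted text, the sponsor's return-product analysis of a test lens cannot begin before database lock, and there is no exception for a SADE or for a deficiency that could have led to one. Sections 9.5, 11.3 and 11.4 therefore do not fit together for the cases where the lens matters most.

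The range of 114 to 122 days is a nominal worst case to last exit under the stated assumptions. It should not be read as a minimum that applies to every event, since an event near the end of the last subject's wear waits only for lock. The conclusion also assumes that no interim procedure exists outside the protocol.

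The primary endpoint and the descriptive effectiveness analysis are not affected. This is a gap in a safety procedure, worth closing because closing it is cheap.

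**What to change.** Reconcile 11.4 with 9.5 and 11.3 by adding one exception to 11.4. For SADEs, and for device deficiencies that could have led to a SADE, the sponsor enters the case in its complaint system and issues the complaint number on receipt of the 24-hour report, and unmasked personnel handle the number and the return. Routine nonserious returns may stay after lock.

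Name the unmasked personnel. Section 7.1 gives the unmasked site coordinator only the task of preparing lenses, so the amendment should not assume that this role already extends to complaint records.

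In the same edit, align the product scope: 9.5 covers every study lens, 11.4 only the Alcon product, and 11.6 sends non-Alcon complaints to the manufacturer. State what happens to an implicated comparator lens.

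The cost is a few sentences in the protocol and a matching entry in the Manual of Procedures. The downside is a small masking risk in the few serious cases, because a complaint number identifies the lens as the test product. If the Manual of Procedures already has such a route, a cross-reference in 11.4 and removal of the conflict with the lock wording would be enough.
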